## 1 PROTOCOL SUMMARY

### 1.1 SYNOPSIS

**Title:** A Phase 2, Randomized, Double-Blind, Placebo-Controlled Study to Evaluate the Efficacy and Safety of Imsidolimab (ANB019) in the Treatment of Subjects with Hidradenitis Suppurativa

**Short Title:** Efficacy and Safety of Imsidolimab in Subjects with Hidradenitis Suppurativa

**Study Description:** This is a Phase 2, multicenter, randomized, double-blind, placebo-controlled study to evaluate the efficacy and safety of imsidolimab in adult subjects with hidradenitis suppurativa (HS). This study also will characterize the pharmacokinetic (PK) profile of imsidolimab and explore the immune response to imsidolimab in subjects with HS.

To be eligible for this study, subjects must have a clinically confirmed diagnosis of HS with a disease duration of at least 6 months before Day 1. In addition, subjects will have the following characteristics at screening and Day 1: 1) HS lesions present in at least 2 distinct anatomical areas, 1 of which must be Hurley Stage II (ie, single or multiple, widely separated, recurrent abscesses with tract formation and cicatrization) or Hurley Stage III (ie, diffuse or near-diffuse involvement, or multiple interconnected tracts and abscesses across the entire area); 2) total abscess and inflammatory nodule (AN) count of  $\geq 5$ ; 3)  $\leq 20$  draining fistulas. Randomization will be stratified based on Hurley Stage at baseline (Stage II or III).

The maximum study duration per subject is approximately 44 weeks, which includes a screening period of up to 30 days, followed by a 16-week placebo-controlled period, a 16-week treatment extension period, and an 8-week follow up period. The placebo-controlled period ends at Day 113 (Week 16) and the treatment extension period starts when study treatment is administered at the Week 16 visit. Of note, during the extension period all subjects will receive imsidolimab but their treatment will remain blinded (see [Figure 1](#)).

During the placebo-controlled period, eligible subjects will be randomized (1:1:1) to receive either imsidolimab (at 1 of 2 different regimens) or placebo, subcutaneously (SC) administered on 4 occasions: Day 1, Day 29 (Week 4), Day 57 (Week 8), and Day 85 (Week 12).

The treatment arms during the placebo-controlled period will be as follows:

1. Imsidolimab 400 mg on Day 1, followed by 200 mg on Days 29, 57, and 85
2. Imsidolimab 200 mg on Day 1, followed by 100 mg on Days 29, 57, and 85

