**Table 1: Schedule of Activities**

	Screening Period			Placebo-Controlled Period			Extension Period			Follow-Up Period		
	Study visit Window (days)	(-30 to -1)	D1	D29 (W4) (±4)	D57 (W8) (±4)	D85 (W12) (±4)	D113 (W16) a (±4)	D141 (W20) (±4)	D169 (W24) (±4)	D197 (W28) (±4)	D225 (W32) (±4)	D253 (W36) (±4)
Informed consent	X											
Demographics	X											
Fitzpatrick skin type classification c	X											
Inclusion and exclusion criteria	X	X										
Medical and surgical history	X	X										
Smoking History c		X										
Height and weight d	X	X				X				X		X
Complete physical examination e	X	X	X	X	X	X				X		X
Vital signs f	X	X	X	X	X	X	X	X	X	X	X	X
12-Lead ECG g	X	X	X			X	X			X		X
Chest X-ray h	X											
Hematology and biochemistry	X	X	X	X	X	X	X	X	X	X	X	X
Urinalysis	X	X	X		X	X	X		X	X		X

Efficacy and Safety of Imsidolimab in Subjects with Hidradenitis Suppurativa  
Protocol ANB019-208

Amendment 1  
24 September 2021

	Screening Period			Placebo-Controlled Period			Extension Period			Follow-Up Period		
	Study visit Window (days)	(-30 to -1)	D1	D29 (W4) (±4)	D57 (W8) (±4)	D85 (W12) (±4)	D113 (W16) a (±4)	D141 (W20) (±4)	D169 (W24) (±4)	D197 (W28) (±4)	D225 (W32) (±4)	D253 (W36) (±4)
TB screening (QuantiFERON®-TB Gold test)	X											
Viral serology	X											
FSH i	X											
Serum pregnancy test (WOCBP only) i	X											X
Urine pregnancy test (WOCBP only) i		X	X	X	X	X	X	X	X	X		
HS Pain NRS, PGIB, PGIS, HS-PtGA, DLQI, HiSQoL j		X	X	X	X	X	X	X	X	X	X	X
PGIC j			X	X	X	X	X	X	X	X	X	X
HS-PGA j	X	X	X	X	X	X	X	X	X	X	X	X
Hurley Stage j	X	X				X				X		X
AN count, draining fistula count, HiSCR j	X	X	X	X	X	X	X	X	X	X	X	X
IHS4 j		X	X	X	X	X	X	X	X	X	X	X
Blood samples for PK k		X	X	X	X	X	X	X	X	X	X	X
Blood samples for ADA k		X	X	X	X	X	X			X		X
Tape strips collection l		X	X			X				X		
Drainage fluid collection l		X	X	X	X	X	X	X	X	X	X	X

	Screening Period			Placebo-Controlled Period			Extension Period			Follow-Up Period			
	Study visit Window (days)	(-30 to -1)	D1	D29 (W4) (±4)	D57 (W8) (±4)	D85 (W12) (±4)	D113 (W16) a (±4)	D141 (W20) (±4)	D169 (W24) (±4)	D197 (W28) (±4)	D225 (W32) (±4)	D253 (W36) (±4)	D281 (W40) EOS/ ET b (±5)
Photography m	X	X	X				X				X		X

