## 9 STATISTICAL CONSIDERATIONS

### 9.1 STATISTICAL HYPOTHESES

The primary analysis for this study is to compare the mean AN count for imsidolimab with placebo during the double-blind treatment period, at a two-sided alpha = 0.10 level. Any testing being performed for secondary or exploratory endpoints will be considered exploratory in nature based on a 2-sided alpha = 0.10

$H_0: \mu_{\text{imsidolimab}} - \mu_{\text{Placebo}} = 0$  vs.  $H_A: \mu_{\text{imsidolimab}} - \mu_{\text{Placebo}} \neq 0$

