### 9.2 SAMPLE SIZE DETERMINATION

Approximately 120 subjects will be randomized in a 1:1:1 ratio to receive one of the following study treatments:

1. Imsidolimab 400 mg on Day 1 followed by 200 mg on Days 29, 57, and 85
2. Imsidolimab 200 mg on Day 1, followed by 100 mg on Days 29, 57, and 85
3. Placebo on Days 1, 29, 57, and 85

For this phase 2 study, the sample size was chosen empirically. Assuming a total of 10% of subjects will discontinue prior to Week 16, there will be approximately 108 evaluable subjects (36 subjects in each arm) at the end of Week 16. The study has 80% power to detect a between-group treatment difference of 4.9 lesions in the primary endpoint of mean change from Baseline in the AN count at Week 16, using a two-sided, equal-variance two-sample t-test at the  $\alpha = 0.10$  level, with the assumption of a common standard deviation (SD) of 8.2 lesions. The assumption was based on PIONEER 1 study (Kimball 2016). Table 6 shows more information on power from a set of scenarios of variability and between-group mean differences.

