## 9.4 STATISTICAL ANALYSES

### 9.4.1 GENERAL APPROACH

The statistical analysis will be performed using SAS® Version 9.4 or higher. All details regarding the statistical analysis and the preparation of tables, listings, and figures will be described in the Statistical Analysis Plan (SAP).

The default summary statistics for continuous variables include number of contributing observations, mean, SD, median, minimum, and maximum. For PK parameters, coefficient of variation (CV) and geometric mean will also be presented, as appropriate.

For categorical variables, the number and percentage (percentage of subjects in each category relative to the total number of subjects in the relevant analysis set or relative to the total number

of subjects in the relevant analysis set with assessments available [where appropriate]) in each category will be the default summary presentation.

Unless otherwise specified, “Baseline” is defined as the last observed value of the parameter of interest prior to the first intake of study treatment (this includes unscheduled visits). For numerical variables, change from Baseline will be calculated as the difference between the value of interest and the corresponding Baseline value. In the analysis of extension study subjects using the Extension Analysis Set, for those subjects who received placebo initially, their baseline will be re-calculated based on the latest data prior to receiving imsidolimab.

Unless otherwise specified, all formal statistical tests will be 2-sided at the 10% significance level. Point estimates of treatment differences will be accompanied with 2-sided 90% confidence intervals (CIs), where applicable.

In the case of normality assumption violations, appropriate nonparametric methods may be used for analysis.

All data will be presented in by-subject listings.

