#### 7.5.1 Primary Efficacy Estimand

The primary estimand, comprising five components, is as follows:

- a) The target population is subjects in the United States and Europe diagnosed for at least 6 months with HS, having lesions at Hurley Stage II or III.
- b) The primary variable is the change from baseline in AN count of an individual subject at Week 16.
- c) To handle intercurrent events such as use of rescue medications, a hypothetical strategy for estimand (**ICH E9, 2019**) will be used such that data collected following receipt of rescue medication (if any) will be considered missing in the analysis. Missing values will be imputed as described in **Section 7.5.4**. The hypothetical scenario envisaged under this estimand is what value the primary variable would have taken if the subject had not taken rescue treatment.

- d) The population-level summary measure for the primary endpoint is mean change from baseline in AN count at Week 16. The estimator for between-group comparison of the primary endpoint will be the difference in the primary endpoint between imidolimab and placebo at Week 16.
- e) The treatment conditions of interest, two imidolimab treatment regimens and one placebo regimen:
  1. Imsidolimab 400 mg injection on Day 1, followed by 200 mg on Days 29, 57, and 85;
  2. Imsidolimab 200 mg injection on Day 1, followed by 100 mg on Day 29, 57, and 85;
  3. Placebo on Days 1, 29, 57, and 85

A linear mixed model will be used for the repeated measures (MMRM) with treatment, visit, treatment by visit interaction, and Hurley Stage at baseline as a categorical covariate and baseline AN count as a continuous covariate. An unstructured correlation (UN) matrix will be used to model correlation within a patient; if convergence is an issue, a Toeplitz structure may be considered. If convergence issue persists, elimination of post-baseline visits other than Week 16 may be considered. Subjects with missing data at Week 16 due to early discontinuation will be included in the model.

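### The primary model adjusts for the last pre-dose AN count but not the screening count; this is valid, but may leave some precision unused

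*Protocol*

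**What the plan says.** Protocol 1.1 and 4.1 set the lesion criteria at two visits: "subjects will have the following characteristics at screening and Day 1". A total AN count of at least 5 is among them. In the Schedule of Activities (protocol Table 1) the row "AN count, draining fistula count, HiSCR" is marked at both screening and Day 1. Protocol 8.1.10 has lesions counted over the whole body at every visit, and protocol 1.3 allows at most 30 days between the two visits.

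Only one of the two counts becomes the baseline. In protocol 9.4.1, Baseline "is defined as the last observed value of the parameter of interest prior to the first intake of study treatment", and SAP Section 6 defines the study baseline in the same way.

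The primary MMRM in protocol 9.4.5 adjusts for Baseline AN count and Hurley Stage. SAP 7.5.1 does the same, with Hurley Stage as a categorical covariate and "baseline AN count as a continuous covariate". The mixed-model template in SAP Appendix 2 has a single BASE term. The sensitivity MMRM in SAP 7.5.4 adds race, smoking, age and Fitzpatrick skin type. The multiple-imputation and tipping-point models in that section use the baseline AN count alone. No planned model uses the screening count beside the Day 1 count.

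**The concern.** A lesion count is a noisy reading of disease level. Protocol 4.2 itself calls HS efficacy assessments highly subjective, and protocol 8.1 asks for one assessor per subject in order to limit variability. When one pre-dose count is an imperfect measure of the underlying level, a second can improve prediction of the Week 16 count. That would lower the residual variance of the treatment contrast.

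The trial expects about 36 evaluable subjects per arm, so a modest gain would be worth having if it cost little. The second count is already collected. As a pre-randomisation covariate it changes neither the estimand nor, if prespecified, the type I error. At stake is the width of the confidence interval for the primary contrast, not its validity.

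**Working it through.** **Inputs from the documents.** The primary test is made "at a two-sided alpha = 0.10 level" (protocol 9.1). Protocol 9.2 states "The study has 80% power to detect a between-group treatment difference of 4.9 lesions", "using a two-sided, equal-variance two-sample t-test at the" 0.10 level, "with the assumption of a common standard deviation (SD) of 8.2 lesions", with 36 evaluable subjects per arm (108 in total). Neither document gives a correlation between AN counts at different visits. Every correlation below is therefore an assumption.

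**Step 1: the plan's own figure.** Noncentrality = 4.9 / (8.2 × √(2/36)) = 2.535, with 70 degrees of freedom. The exact noncentral t gives 80.7% power, so the stated 80% reproduces.

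**Step 2: equal correlation r among screening, Day 1 and Week 16.** With one count the residual variance is proportional to 1 − r². With two it is proportional to 1 − 2r²/(1+r). The ratio is (1+2r)/(1+r)².

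| r | Variance ratio | Reduction | Power at 4.9 if 8.2 is the residual SD |
|---|---|---|---|
| 0.4 | 0.918 | 8% | 83.5% |
| 0.5 | 0.889 | 11% | 84.6% |
| 0.6 | 0.859 | 14% | 85.6% |
| 0.7 | 0.830 | 17% | 86.7% |

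At r = 0.7 the subject equivalent is 108 × (1 − 0.83), or about 18 of 108 evaluable subjects.

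**Step 3: correlation that decays with time.** Let a = corr(Day 1, Week 16), b = corr(screening, Week 16) and c = corr(screening, Day 1). Then R² = (a² + b² − 2abc)/(1 − c²), and the variance ratio is (1 − R²)/(1 − a²).

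| c | a | b | Variance ratio |
|---|---|---|---|
| 0.75 | 0.60 | 0.45 | 1.000 |
| 0.70 | 0.60 | 0.50 | 0.980 |
| 0.80 | 0.60 | 0.55 | 0.979 |
| 0.60 | 0.50 | 0.45 | 0.953 |
| 0.70 | 0.60 | 0.55 | 0.948 |
| 0.60 | 0.55 | 0.55 | 0.892 |

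Over c from 0.6 to 0.8, a from 0.5 to 0.6 and b from 0.45 to 0.55, with b no larger than a, the reduction runs from 0% to about 11%. It is exactly zero when b = a × c. The first row shows this: 0.60 × 0.75 = 0.45.

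**Step 4: cost of the extra parameter.** The approximate variance inflation is (108 − 5 − 2)/(108 − 6 − 2) = 101/100 = 1.01, or about 1%.

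**Step 5: power under the two readings of 8.2.**

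- *8.2 as the residual SD after Day 1 adjustment.* Power is 80.7% with one count. It becomes 81.4% for a 2% variance gain, 82.4% for 5%, and 86.7% at a ratio of 0.83.
- *8.2 as the SD of the unadjusted change.* Protocol 9.2 uses it this way, in a t-test without covariates. With equal variances at the two visits, adjusting for Day 1 gives a residual SD of 8.2 × √((1+r)/2). That is 6.86 at r = 0.4 and 7.56 at r = 0.7, so the planned model already has 91.2% and 86.0% power. A 2% variance gain raises these to 91.7% and 86.6%, and a 5% gain to 92.4% and 87.5%: about 0.5 to 1.5 points.

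**The case against.** The strongest reply is that nothing is wrong. A baseline-adjusted MMRM with Hurley Stage is a sound prespecified analysis, the sample size reproduces, and a short covariate list is a legitimate choice. All of that stands.

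The documents also give reasons to expect a gain towards the low end:

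- Protocol 8.1 stresses the same assessor at Day 1 and Week 16 in particular, so the screening count may more often carry assessor differences.
- The 2- and 4-week washouts in protocol Table 4 can fall inside the 30-day screening window, so some screening counts may be taken on, or just off, HS therapy. The 6-week stability criterion only partly offsets this.
- Requiring at least 5 lesions at both visits restricts the range and tends to weaken correlation.
- Hurley Stage is already in the model, and the formulas above ignore any persistent severity that it captures.

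Zero gain is not a curiosity either. It is what first-order autoregressive decay produces, and the lost degree of freedom would then make the net effect slightly negative.

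A reader might go further than the documents allow in three ways. The first is to conclude that the primary analysis is flawed or the trial underpowered; Steps 1 and 5 do not support that. The second is to treat a lower variance as assured, which no figure in the documents establishes. The third is to put the gain at 22 subjects. That is 108/0.83 − 108 = 22, taken from r = 0.7, and it counts subjects who would have to be added to the planned model to match the better precision. The saving from 108 is about 18, and it belongs to the favourable end only.

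**Conclusion.** The point holds as a low-cost improvement, not as an error. The screening AN count is required and scheduled for every subject, and no planned model uses it beside the Day 1 count. The planned analysis is valid without it.

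The gain cannot be derived from the documents. Under the assumptions shown, it lies between nothing and 17% of residual variance, less about 1% for the added parameter. Decaying correlations, which are the more cautious case, give 0% to about 11%. In power terms, a 2–5% variance gain is worth roughly 0.5 to 2 points, depending on how 8.2 is read. The rise to about 87% needs both an equal correlation of 0.7 across all three visits and 8.2 read as a residual SD, which is not how protocol 9.2 uses it.

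**What to change.** Before unblinding, keep change from the Day 1 baseline as the response, and keep baseline AN count and Hurley Stage in the model. Prespecify the screening AN count as a second continuous covariate in SAP 7.5.1 and in the MODEL line of the Appendix 2 mixed-model template. That line must also carry BASEHSSTAGE, which the template now lists only in the CLASS statement. Record the departure from protocol 9.4.5 in SAP Section 8. The multiple-imputation and tipping-point analyses refit the 7.5.1 model, so their imputation models should carry the same covariate.

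If either pre-dose count is missing, set it to the available one. Both are pre-dose values, so the rule does not depend on response to treatment. Where the Day 1 count is missing, the baseline definition already falls back to the screening value, and the two covariates simply coincide for that subject.

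The cost is one degree of freedom and a documented SAP change, with no new data. The downside is that the gain may turn out to be near zero. If the sponsor prefers the shorter model, a sentence giving the reason would be enough.

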## 1.2 SCHEMA

Figure 1: ANB019-208 Study Schema

a During the placebo-controlled period, subjects will be randomized (1:1:1) to receive either imsidolimab (at 1 of 2 different regimens) or placebo, SC administered on 4 occasions: 1) 400-mg dose of imsidolimab on Day 1, 200-mg dose of imsidolimab on Days 29, 57, and 85; 2) 200-mg dose of imsidolimab on Day 1, 100-mg dose of imsidolimab on Days 29, 57, and 85, 3) placebo on Days 1, 29, 57, and 85.

b The placebo-controlled period ends on Day 113 (Week 16) visit, before study treatment administration. Predose assessments performed on Day 113 (Week 16) will be used to evaluate the primary and secondary efficacy endpoints, as well as the safety, tolerability, and immune response of imsidolimab compared with placebo. The extension period starts when the study treatment is administered on Day 113 (Week 16) visit. All subjects will receive imsidolimab SC administered on 4 occasions during the extension period.

c Subjects in Arm 3 randomized to placebo during the placebo-controlled period will be randomized 1:1 to receive either a 400-mg dose of imsidolimab on Day 113, followed by a 200-mg dose on Days 141, 169, and 197; or a 200-mg dose of imsidolimab on Day 113, followed by a 100-mg dose of imsidolimab on Days 141, 169, and 197. Subjects randomized to imsidolimab in Arms 1 and 2 during the placebo-controlled period will continue to receive the same maintenance dose of imsidolimab (200 mg or 100 mg) on Days 113, 141, 169, and 197.

### 1.3 SCHEDULE OF ACTIVITIES

The screening evaluation will only be performed after the subject has agreed to participate and has signed and dated the ICF. No treatment or study-related procedures will be initiated before the informed consent is signed. The Day 1 visit must be performed, at the latest, 30 days after the screening visit.

The screening evaluation will be performed according to the inclusion and exclusion criteria. If the subject fulfills all inclusion criteria and no exclusion criteria, he or she may be included in the study.

**Table 1** provides a description of the procedures to be performed at each visit during the study.

Of note, the placebo-controlled period ends at Day 113 (Week 16). Predose assessments performed at Day 113 (Week 16) will be used to evaluate the primary and secondary efficacy endpoints, and safety, tolerability, and immune response of imsidolimab compared with placebo. The treatment extension period starts when study treatment is administered at the Week 16 visit. All subjects will receive imsidolimab during the treatment extension period.

Unless specified otherwise, the study assessments scheduled on Day 1 must be performed before study treatment administration. The recommended order for performing the study assessments is as follows (applicable to all visits):

- Subject-reported questionnaires (worst HS Pain NRS should be performed before average HS Pain NRS)
- Efficacy assessments (global assessments [eg, HS-PGA] should be performed before more quantitative assessments [eg, abscess and inflammatory nodule (AN) count])
- Physical examination
- ECG
- Vital signs
- Blood samples collection (for safety, PK, ADA)
- Photography (may be performed anytime predose provided it is before skin sample collection)
- Tape stripping

The COVID-19 pandemic may impact the ability to adhere to the study procedures described in **Table 1** due to challenges that include, but are not limited to, subject preferences, site closures, travel restrictions, and quarantines. Please refer to **Section 4.5** for more details on allowable, as necessary, modifications to the protocol due to COVID-19 restrictions, including conducting optional home visits when on-site study visits are considered not feasible. Such modifications in study conduct always must be in accordance with local regulations/mandates.

**Table 1: Schedule of Activities**

	Screening Period			Placebo-Controlled Period			Extension Period			Follow-Up Period		
	Study visit Window (days)	(-30 to -1)	D1	D29 (W4) (±4)	D57 (W8) (±4)	D85 (W12) (±4)	D113 (W16) a (±4)	D141 (W20) (±4)	D169 (W24) (±4)	D197 (W28) (±4)	D225 (W32) (±4)	D253 (W36) (±4)
Informed consent	X											
Demographics	X											
Fitzpatrick skin type classification c	X											
Inclusion and exclusion criteria	X	X										
Medical and surgical history	X	X										
Smoking History c		X										
Height and weight d	X	X				X				X		X
Complete physical examination e	X	X	X	X	X	X				X		X
Vital signs f	X	X	X	X	X	X	X	X	X	X	X	X
12-Lead ECG g	X	X	X			X	X			X		X
Chest X-ray h	X											
Hematology and biochemistry	X	X	X	X	X	X	X	X	X	X	X	X
Urinalysis	X	X	X		X	X	X		X	X		X

Efficacy and Safety of Imsidolimab in Subjects with Hidradenitis Suppurativa  
Protocol ANB019-208

Amendment 1  
24 September 2021

	Screening Period			Placebo-Controlled Period			Extension Period			Follow-Up Period		
	Study visit Window (days)	(-30 to -1)	D1	D29 (W4) (±4)	D57 (W8) (±4)	D85 (W12) (±4)	D113 (W16) a (±4)	D141 (W20) (±4)	D169 (W24) (±4)	D197 (W28) (±4)	D225 (W32) (±4)	D253 (W36) (±4)
TB screening (QuantiFERON®-TB Gold test)	X											
Viral serology	X											
FSH i	X											
Serum pregnancy test (WOCBP only) i	X											X
Urine pregnancy test (WOCBP only) i		X	X	X	X	X	X	X	X	X		
HS Pain NRS, PGIB, PGIS, HS-PtGA, DLQI, HiSQoL j		X	X	X	X	X	X	X	X	X	X	X
PGIC j			X	X	X	X	X	X	X	X	X	X
HS-PGA j	X	X	X	X	X	X	X	X	X	X	X	X
Hurley Stage j	X	X				X				X		X
AN count, draining fistula count, HiSCR j	X	X	X	X	X	X	X	X	X	X	X	X
IHS4 j		X	X	X	X	X	X	X	X	X	X	X
Blood samples for PK k		X	X	X	X	X	X	X	X	X	X	X
Blood samples for ADA k		X	X	X	X	X	X			X		X
Tape strips collection l		X	X			X				X		
Drainage fluid collection l		X	X	X	X	X	X	X	X	X	X	X

	Screening Period			Placebo-Controlled Period			Extension Period			Follow-Up Period			
	Study visit Window (days)	(-30 to -1)	D1	D29 (W4) (±4)	D57 (W8) (±4)	D85 (W12) (±4)	D113 (W16) a (±4)	D141 (W20) (±4)	D169 (W24) (±4)	D197 (W28) (±4)	D225 (W32) (±4)	D253 (W36) (±4)	D281 (W40) EOS/ ET b (±5)
Photography m	X	X	X				X				X		X
Randomization n			X				X						
Study treatment administration o			X	X	X	X	X	X	X				
AE/SAE review	X												Continuously
Concomitant medication review p	X												Continuously

Abbreviations: ADA, anti-drug antibody; AE, adverse event; AN, abscess and inflammatory nodule; D, day; DLQI, Dermatology Life Quality Index; ECG, electrocardiogram; EOS, end of study; ET, early termination; FSH, follicle-stimulating hormone; HiSCR, Hidradenitis Suppurativa Clinical Response; HSQoL, Hidradenitis Suppurativa Quality of Life; HS, hidradenitis suppurativa; HS-PGA, Hidradenitis Suppurativa Physician Global Assessment; HS-PtGA, Hidradenitis Suppurativa Patient Global Assessment; IHS4, International Hidradenitis Suppurativa Severity Score System; NRS, Numeric Rating Scale; PGIB, Patient Global Impression of Bother; PGIC, Patient Global Impression of Change; PGIS, Patient Global Impression of Severity; PK, pharmacokinetics; SAE, serious adverse event; SC, subcutaneously; SoA, Schedule of Activities; TB, tuberculosis; W, week; WOCBP, woman of childbearing potential.

a All subjects will receive imsidolimab during the extension period starting on Day 113 (Week 16) visit until Day 197 (Week 28) visit. The placebo-controlled period ends on Day 113 (Week 16) visit, before study treatment administration. The extension period starts when the study treatment is administered on Day 113 (Week 16) visit.

b The ET visit will include all procedures to be done at the EOS visit (Day 281/Week 40 visit).

c If the Fitzpatrick skin type and/or Smoking history are not collected at screening and D1 respectively, they may be collected at any subsequent visit.

d Height to be measured at screening only for subjects.

e Refer to [Section 8.2.4](#) for details regarding the complete physical examination.

f Refer to [Section 8.2.5](#) for details and instructions regarding vital signs.

g Refer to [Section 8.2.6](#) for details and instructions regarding the ECG. In addition to the time points specified in the SoA, ECGs may be performed at any time during the study if in the opinion of the Investigator it is clinically warranted.

h Bidirectional posterior-anterior view and lateral view chest X-ray will be performed at screening. If a chest X-ray was performed within 6 months of screening and no clinically significant abnormality was observed, it can be skipped at screening.

- i The FSH testing is performed for women not of childbearing potential who are postmenopausal (at least 12 months of amenorrhea without an alternative medical cause). Additional pregnancy testing may be performed whenever a menstrual cycle is missed or when pregnancy is otherwise suspected. Refer to [Appendix 11](#) for details and instructions regarding clinical laboratory parameters.
- j Refer to [Section 8.1](#) for details and instructions on AN count, draining fistula count, HiSCR, Hurley Stage, HS-PGA, IHS4, HS Pain NRS, PGIC, PGIB, PGIS, DLQI, HS-PtGA, and HiSQoL. From screening through Week 32, subjects will not be permitted to use any analgesics related to HS pain within 24 hours of a scheduled study visit. Subjects may use analgesics after the questionnaires are completed at the study visit.
- k Sample for PK will be collected predose. See [Table 5](#) for PK and ADA sample collection time points.
- l Tape stripping will be performed for all randomized subjects as part of this study (not optional). Tape strips will be collected from non-lesional and lesional skin at Day 1 and Week 16 and from lesional skin at Week 4 and Week 32. Drainage fluid may be collected (optional) at any visit after screening in which HS lesional drainage is present, and stored for future biomarker analysis.
- m Photography (of representative lesion[s], fistulas, and scarring) is an optional procedure for all subjects at each of the specified visits at selected site. Two images from two distinct regions of highest density inflammatory nodules/abscesses/fistulas should be taken at baseline if possible. The anatomic regions should be identifiable from the images. These regions should be recorded and consistently photographed throughout the duration of the study if possible.
- n Starting at Day 113 (Week 16), subjects who received placebo during the placebo-controlled period will be randomized 1:1 to receive imsidolimab at 1 of 2 different regimens. Subjects who received imsidolimab during the placebo-controlled period will not be randomized at the Week 16 visit.
- o During the placebo-controlled period, subjects will receive either imsidolimab or placebo SC administered as follow according to randomization arm:1) 400-mg dose of imsidolimab on Day 1; followed by 200-mg dose of imsidolimab on Days 29, 57, and 85; 2) 200-mg dose of imsidolimab on Day 1; followed by a 100-mg dose of imsidolimab on Days 29, 57, and 85; 3) placebo. The placebo-controlled period ends at the Day 113 (Week 16) visit, before study treatment administration. During the extension period, subjects assigned to imsidolimab during the placebo-controlled period will continue to receive the same maintenance dose of imsidolimab, 200 mg or 100 mg. Subjects assigned to placebo during the placebo-controlled period will receive either a 400-mg dose of imsidolimab on Day 113, followed by 200-mg doses of imsidolimab on Days 141, 169, and 197; or a 200 mg dose of imsidolimab on Day 113, followed by 100-mg doses of imsidolimab on Days 141, 169, and 197.
- p At screening, prior medications should be reviewed and documented. Refer to [Section 6.5](#).

